8.10. PTC Therapeutics Adverse Event Reporting Requirements

As the sponsor of the study, PTC Therapeutics is responsible for reporting certain safety information, particularly SAEs and patient deaths related to participation in the study, to each investigator in an expedited manner. If notification of an adverse event requiring expedited reporting to investigators is received, PTC Therapeutics or its designated representative will contact each investigator site participating in this study by e-mail, fax, and/or overnight mail such that the investigator can promptly notify the site IRB/IEC per their local requirements. The initial expedited safety report will be provided as required according to local regulations (eg, within 15 days) after the earliest date PTC Therapeutics or an agent of PTC Therapeutics (eg, a site monitor) becomes aware of an adverse event. This awareness date is the date the regulatory reporting clock begins and the date is considered Day 0.

9. WITHDRAWAL OF PATIENTS

All patients who receive study drug should remain in the study whenever possible. However:

- The patient has the right to withdraw consent and discontinue study drug at any time.
- If the patient's condition substantially worsens after initiating study drug, the patient will be carefully evaluated by the investigator in consultation with the PTC Therapeutics medical monitor. This worsening may include cardiac events such as QTc interval limits, new evidence of symptomatic cardiomyopathy and significant decrease in left ventricular ejection fraction. The patient will be withdrawn from treatment if continuing would place them at risk.
- Upon consultation with the PTC Therapeutics medical monitor, the investigator may withdraw the patient from study drug, if, in the investigator's clinical judgment, it is not in the patient's best interest to continue.
- If the patient becomes significantly noncompliant with study drug administration, study procedures, or study requirements. In this event, the patient should be withdrawn from study treatment when the circumstances surrounding noncompliance increase risk to the patient or are anticipated to substantially compromise the interpretation of study results.
- The patient will be withdrawn from treatment if he is unable to tolerate study drug.
- This study may be discontinued by the relevant regulatory authority and/or PTC Therapeutics at any time.
- This study may be stopped upon ataluren marketing authorization within the relevant country.

The date study drug is discontinued and the reason for discontinuation will be recorded in the source documents and in the eCRF. The PTC medical monitor (and designee) should be informed via e-mail of when a patient is discontinues study drug.

When study drug is discontinued (regardless of the reason), the investigator should encourage that all of the evaluations required at the End of Treatment Visit be performed and that any additional evaluations be completed that may be necessary to ensure that the patient is free of

untoward effects. The patient should be encouraged to seek appropriate follow-up for any continuing health problems.

10. STATISTICS AND DATA MANAGEMENT

10.1. Sample Size Calculation

The sample size for this extension study is not based upon any formal statistical hypothesis, but its upper bound is determined by the requirement that patients must have participated in the previous Phase 3 study of PTC124 (PTC124-GD-020-DMD) in which ~ 220 patients are expected to be enrolled.

10.2. Study Population Definition

10.2.1. Safety Population

The safety population consists of all patients who took at least one dose of ataluren. This population will be used to analyze safety and treatment administration.

10.2.2. Evaluable Populations

In general, evaluable populations consist of all as-treated patients who have sufficient data to assess the measure of interest (eg, ataluren plasma concentrations, Activities of Daily Living/Disease Status Survey). These populations may be evaluated in the analysis of other secondary endpoints.

10.3. General Statistical Considerations

By-patient listings will be created for each CRF module. Summary tables for continuous variables will contain the following statistics: n, mean, standard deviation, standard error, 95% confidence intervals (CIs) on the mean, median, minimum, and maximum. Summary tables for categorical variables will include N, n, percentage, and 95% CIs on the percentage. Where applicable, the summary data (mean, standard error) will be presented in graphical form of against time of visit.

Unless otherwise specified, all analyses will be 2-sided at the 0.05 level of significance.

10.4. Specific Statistical Analyses

10.4.1. Study Conduct and Patient Disposition

The number of patients in each of the analyzed study populations and the patients completing all planned assessments during the study will be described. Patients who discontinue study drug or are removed from the study prematurely will also be reported.

10.4.2. Use of Concomitant Medication and Supportive Therapy

Concomitant medications will be coded by means of the World Health Organization Drug Dictionary (WHODRUG) dictionary into Anatomical-Therapeutic-Chemical classification

(ATC) codes. The type and timing of use of specific concomitant medications will be listed and summarized.

Specific attention will be focused on corticosteroid use. The type and duration of pre-study use will be described. The type, dose, schedule, duration of use, dose modifications, dose omissions, and reasons for deviations from initial therapy will be described.

10.4.3. Primary Variables – Safety

Vital signs (height, weight, systolic and diastolic blood pressure, radial pulse rate, and body temperature) and physical examination data will be listed and summarized by visit and overall. Where appropriate, changes from baseline at each visit will be summarized and tested by means of the paired t-test or a nonparametric alternative.

Adverse events will be classified using the MedDRA classification system. The severity of adverse events will be graded according to the CTCAE, Version 3.0, whenever possible.

The frequency of patients experiencing a specific adverse event will be tabulated by treatment period and for the whole study, categorizing events by body system, and MedDRA term. In the by-patient analysis, a patient having the same event more than once will be counted only once. Adverse events will be summarized by worst CTCAE grade within a patient.

Adverse events classified as CTCAE Grade 3 or higher; study-drug-related events; adrenal, hepatic, and renal events leading to special diagnostic evaluations; events leading to discontinuation from treatment; and SAEs will be considered with special attention.

No attempt will be made to reconcile data collected from the patient/caregiver-reported outcome instruments with adverse event reporting.

Hematological data will be summarized by treatment period and overall. Hematological data will be graded according to CTCAE severity grade. The frequencies of the worst severity grade observed will be displayed by worst CTCAE grade within a patient.

Serum biochemistry and urine data (including parameters for assessment of adrenal, hepatic, and renal monitoring – see [Section 6.3.1](#)) will be summarized by treatment period and overall. Values will be graded according to CTCAE severity grade, when applicable. For variables graded according to CTCAE severity grade, the frequencies of the worst severity grade observed will be displayed within a patient. For parameters for which a CTCAE scale does not exist, the frequency of patients with values below, within, and above the normal ranges will be summarized.

Urinalysis data will be listed and summarized by treatment period and overall, and will be checked for changes from baseline over time.

The results of an ultrasound to examine the kidneys and collecting system will be listed and abnormal results will be noted and investigated in terms of their relation to other relevant patient outcome measurement.

ECG data will be listed and summarized by treatment period and overall, and will be checked for changes from baseline over time.

10.5. Secondary Endpoints

10.5.1. 6 Minute Walk Test

The 6 minute walk distance (6MWD) results, as well as their changes from baseline will be described by patient and visit and summarized by visit. The within patient changes from baseline will be tested for each applicable visit using the paired t test.

Supportive analyses will include:

- An ordinary ANCOVA (again after multiple imputation for missing values) will be applied. The model will include the stratification factors as strata and baseline as a covariate.
- An analysis of time to persistent 10% worsening using Kaplan-Meier method and Cox regression
- A repeat of the primary ANCOVA analysis on the 6MWD after it has been converted to percent-predicted 6MWD by means of a relevant reference equation [Geiger 2007]
- A comparison of the percentage of responders (<10% worsening of 6MWD at Week 48) and progressors (\geq 10% worsening of 6MWD at Week 48)
- An exploration of the treatment effect in 6MWD in the context of the following:
 - o the protocol-specified stratification factors
 - o baseline height, baseline weight, and baseline BMI
 - o Stop codon type
 - o Exon location

In all relevant analyses, compliant patients who become nonambulatory (unable to perform the 10 meter run/walk test in \leq 30 seconds) during the study will be assigned a 6MWD of zero from the timepoint at which the patient becomes nonambulatory.

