10.5.2. Timed Function Tests (TFTs)

The results of the timed function tests (the time taken to stand from a supine position, time taken to run/walk 10 meters, and time taken to climb/descend 4 standard-sized stairs) in those patients who have the ability, as well as the changes from baseline will be described by patient and visit and summarized by visit and overall. The within patient changes from baseline will be tested for each applicable visit using the paired t-test. Patients who cannot perform a test within 30 seconds will be assigned 30 seconds as their result.

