## **4. STUDY POPULATION**

- As-Treated population: All subjects who receive at least 1 dose of ataluren treatment in the extension phase. This population will be evaluated in the analyses of safety and efficacy.
- PK population: All subjects who has at least one PK concentration data. This population will used for the PK concentration and parameter summary.

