## 5.6. Study Drug Exposure and Compliance

Study drug compliance will be assessed in terms of the percentage of drug actually taken relative to the amount that should have been taken during the study. Treatment duration (weeks) will be calculated as  $(\text{last dose date} - \text{first dose date} + 1)/7$ , if date of last study drug intake was not known:  $(\text{last visit date} - \text{first dose date} + 1)/7$ . The summary of the overall compliance and treatment duration will be represented for overall subjects and a subgroup of ambulatory/non-ambulatory subjects at study entry.

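### The rule scoring loss of ambulation as 0 m covers only 'compliant' boys, a term left undefined, so visit-mean 6MWD can only be too high or unchanged

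*Protocol*

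**What the plan says.** **The rule.** Protocol 10.5.1 reads "In all relevant analyses, compliant patients who become nonambulatory" (defined as failing the 10-metre run/walk within 30 seconds) "will be assigned a 6MWD of zero from the timepoint at which the patient becomes nonambulatory". It gives no value for a boy who becomes nonambulatory and is not compliant.

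**Compliance.** Neither document says what makes a patient compliant for this rule. Protocol 9 treats noncompliance broadly as a ground for withdrawal: "If the patient becomes significantly noncompliant with study drug administration, study procedures, or study requirements". It sets no threshold. SAP 5.6 is narrower: "Study drug compliance will be assessed in terms of the percentage of drug actually taken relative to the amount that should have been taken". It sets no cut-off either.

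**Who is analysed.** Protocol 10.2.2 says that "evaluable populations consist of all as-treated patients who have sufficient data to assess the measure of interest". SAP 4 takes "All subjects who receive at least 1 dose of ataluren treatment in the extension phase" and adds: "This population will be evaluated in the analyses of safety and efficacy". Neither definition has a compliance condition.

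**Parallel rules.** For the timed function tests, Protocol 10.5.2 says "Patients who cannot perform a test within 30 seconds will be assigned 30 seconds as their result". SAP 5.8.4 caps the 10-metre run/walk and the supine-to-stand time at 30 seconds. SAP 5.8.5 scores an NSAA activity zero when it is lost through progression or loss of ambulation. None of these depends on compliance.

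**What the SAP does with 6MWD.** SAP 5.8.3 keeps descriptive summaries by visit, of change from baseline and by age. It neither repeats nor drops the zero rule. SAP 7 removes the supportive 6MWT analyses and the paired t-tests and does not mention the rule. SAP 1 gives the SAP precedence only where the two documents conflict.

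**The concern.** Under the written rule, the handling of a boy depends jointly on compliance and outcome. A noncompliant boy who still walks contributes his measured distance, while a noncompliant boy who has stopped walking is not given the zero that a compliant boy in the same state receives. That is not an on-treatment analysis, because noncompliant walkers stay in. Nor does it follow all boys regardless of adherence, because the rule withholds the worst score from some of them.

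Compliance is also observed after baseline. A boy who is progressing may find visits, tests or dosing harder to keep up, so the condition may be related to the outcome it qualifies. With no definition and open-label data, the classification could be settled after the walking results are known.

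At stake is how far the by-visit 6MWD summaries, the ambulation secondary endpoint, reflect boys who lose the ability to walk.

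**Working it through.** The documents give no figure to reproduce, so this checks direction first and then size.

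**Direction.** A 6MWD cannot be below 0 m. Start from zero for every nonambulatory boy and change the handling of the noncompliant ones:
- Kept with a measured or imputed distance of at least 0 m: each value rises or stays the same, so the mean does too.
- Left missing: removing zeros from a set of non-negative values raises the mean or leaves it unchanged.

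The same holds for change from baseline when a distance is kept. When the boy is missing, it holds as long as his baseline distance (his loss if scored 0 m) exceeds the mean decline of those retained, as would be expected.

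**Inputs, all assumed:**
- m = 330 m, the mean 6MWD of boys still walking at a visit.
- L = 0.10, 0.20 or 0.40, the share nonambulatory at that visit.
- c = 0, 0.05, 0.10 or 0.25, the share of nonambulatory boys classed noncompliant.

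**Formulas:**
- Zero for all: (1 − L)m.
- Zero for compliant boys only, the others missing: (1 − L)m / (1 − Lc).
- Others keep a short distance d: (1 − L)m + Lcd, so the overstatement is Lcd.

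**Results with the others missing** (mean, and difference from zero for all):

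| L | Zero for all | c = 0.05 | c = 0.10 | c = 0.25 |
|---|---|---|---|---|
| 0.10 | 297.0 m | 298.5 m (+1.5) | 300.0 m (+3.0) | 304.6 m (+7.6) |
| 0.20 | 264.0 m | 266.7 m (+2.7) | 269.4 m (+5.4) | 277.9 m (+13.9) |
| 0.40 | 198.0 m | 202.0 m (+4.0) | 206.25 m (+8.25) | 220.0 m (+22.0) |

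At c = 0 every difference is 0. As an example, L = 0.20 and c = 0.10 give 264 / (1 − 0.02) = 269.4 m. With the upper bound of about 220 patients, that is 0.02 × 220 = 4.4 boys.

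**If a short distance is still recorded.** With d = 50 m (assumed), L = 0.20 and c = 0.10 give 0.20 × 0.10 × 50 = 1.0 m. The extremes of the grid give 0.10 × 0.05 × 50 = 0.25 m and 0.40 × 0.25 × 50 = 5.0 m.

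**Scale.** Protocol 14.2 treats 30 m as clinically important, but as a difference from placebo, so it is only a rough yardstick for a single-arm mean. To reach 30 m with the others missing, (1 − L)m × Lc / (1 − Lc) must equal 30. At L = 0.40 this gives Lc = 30 / 228 = 0.132, so c ≈ 0.33. At L = 0.20 it gives Lc = 30 / 294 = 0.102, so c ≈ 0.51.

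**The case against.** **Exclusion is not written.** A reader might infer that noncompliant boys who stop walking are dropped and that 6MWD is therefore overstated. The protocol does not say so. Its threshold of 10 m in 30 seconds is a pace of 120 m over six minutes (10 × 360 / 30), so a slower boy might still record a distance. The protocol's ANCOVA used multiple imputation, although SAP 7 removes that analysis. If no such boy is noncompliant, nothing changes. This stands, and it is why the conclusion is too high or unchanged.

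**Noncompliant walkers may also leave.** Protocol 9 calls for withdrawal from treatment when noncompliance raises risk or threatens interpretation. This narrows the asymmetry. It does not remove it, because lesser noncompliance leads to no withdrawal.

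**Noncompliance may be rare.** Protocol 2.2.3 reports over 99% of planned doses taken on average in the Phase 2a study and median compliance above 97% per arm in Phase 2b. On a drug-percentage definition, the low end of the table is then more plausible. The figures say less about a definition that includes procedures and requirements, or about treatment of up to 144 weeks.

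**The SAP may have replaced the rule.** SAP 5.8.3 states no zero rule, and a reader might infer that the protocol's no longer applies. But SAP 7 does not list it as removed, and silence is not clearly a conflict. The protocol wording can still govern the retained summaries. Whether the SAP scores any boy 0 m is a separate and possibly larger question; reinstating the protocol wording unchanged would bring this condition back with it.

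**A bias in favour of the drug.** This too goes beyond the documents. The SAP plans no hypothesis test on 6MWD. The registry comparison methods specified in SAP 8.3 concern FVC and age at loss of ambulation, and SAP 1 places that work outside the CSR. Loss of ambulation is also reported without a compliance condition through the Kaplan-Meier analysis, timed tests and NSAA.

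**Conclusion.** The point holds in a limited form. The only stated 6MWD rule for loss of ambulation depends on an undefined post-baseline status that the analysis populations and the parallel timed-test and NSAA rules do not use. Relative to zero for all, visit-mean 6MWD can only be overstated or unchanged, and the same is expected of change from baseline.

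The size cannot be fixed from the documents. It rests on the assumed walker mean, nonambulatory share and noncompliant share, and on those boys being missing. Across the grid it runs from nil to 22.0 m, and it is smaller where a short distance is recorded. It reaches 30 m only if noncompliance among nonambulatory boys is high. The effect is confined to a descriptive, single-arm secondary endpoint; the primary safety objective is unaffected. The change is still worth making, because the condition alters how patients are scored and is cheap to remove.

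**What to change.** - Delete the word 'compliant' from the rule in Protocol 10.5.1.
- State in SAP 5.8.3 that every boy is assigned 0 m from the visit at which he becomes nonambulatory, regardless of compliance.
- List this in SAP 7 as a change from the protocol.
- Report at each visit the number of boys assigned zero and the number missing.
- If a compliance-based view is wanted, present it as a sensitivity summary with a defined cut-off that drops noncompliant walkers and non-walkers alike.

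The cost is one word in the protocol, about two sentences in the SAP and two counts per visit, with no new data collection. The SAP records that the sponsor has decided to discontinue the study, so the SAP text matters most in practice. The downside for the sponsor is a slightly less favourable reported mean if any noncompliant boy lost ambulation.

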10.5.2. Timed Function Tests (TFTs)

The results of the timed function tests (the time taken to stand from a supine position, time taken to run/walk 10 meters, and time taken to climb/descend 4 standard-sized stairs) in those patients who have the ability, as well as the changes from baseline will be described by patient and visit and summarized by visit and overall. The within patient changes from baseline will be tested for each applicable visit using the paired t-test. Patients who cannot perform a test within 30 seconds will be assigned 30 seconds as their result.

10.5.3. North Star Ambulatory Assessment (NSAA)

The NSAA consists of 17 activities, each scored as 0, 1, or 2. The sum of these 17 scores will be used to form a total score. The changes from baseline will be described by patient and visit and summarized by visit and overall.

10.5.4. Pediatric Outcomes Data Collection Instrument (PODCI) Transfers/Basic Mobility and Sports/Physical Functioning scores

The two PODCI domains (transfers/mobility and sports participation) each provide a numerical score from 0-100. Changes from baseline will be described by patient and visit and summarized by visit and overall.

10.5.5. Performance Upper Limb (PUL) Assessment

The PUL assessment includes 22 items (with an entry item to define starting functional level to avoid testing functional dimensions in which the patient lacks the lower limit of function, and 21 items subdivided into shoulder level (4 items), elbow level (9 items), and distal level (8 items) dimensions. Scoring varies across the scale between 0-1 to 0-6 according to performance. Each dimension will be scored separately with a maximum score of 16 for shoulder level, 34 for elbow level, and 24 for distal level. Total score will be calculated by adding the 3 level scores (maximum global score of 74). Changes from baseline will be described by patient and visit and summarized by visit and overall.

10.5.6. Activities of Daily Living/Disease Status Survey

Disease status survey data will be listed by patient and visit. Changes from baseline to each scheduled visit and to the final visit will be summarized descriptively.

10.5.7. Spirometry

Pulmonary function parameters (adjusted as appropriate for gender, age, and height (using ulna length and arm span) and their changes from baseline will be described by patient and visit and summarized by visit. Ulna length and arm span will be used for separate calculation of %-predicted parameters. The within-patient changes from baseline will be tested for each applicable visit using the t-test. Repeated measure analysis may also be used to estimate the effect of treatment duration on pulmonary function parameters.

10.5.8. Ataluren Plasma Concentrations

Ataluren plasma concentrations collected prior to the morning dose will be summarized. The relationship between ataluren plasma concentrations and selected efficacy and safety outcomes will be explored. Results will be placed into context with PK data from previous studies.

If needed, data regarding concentrations of major and/or active metabolites in retained plasma samples will be summarized and potential correlations with safety variables will be investigated.

10.5.9. Exploration of Correlations

Correlations between patient characteristics and outcome measures and correlations among outcomes measures may be explored using regression models or other appropriate techniques.

11. STUDY COMMITTEES

11.1. Study Steering Committee

A study steering committee (SSC) will be responsible for protocol development, review of any study amendments, and coordination of study conduct and interpretation of results. The SSC comprises the PTC Therapeutics medical monitor and biostatistician for the study, the PTC Therapeutics chief medical officer and experts in DMD. Other specialists may be invited to participate as members of the SSC at any time if additional expertise is desired. The activities of this committee are described in a charter.

